10.1. Primary Efficacy Estimands and Analysis

The main estimand and the second estimand for the primary efficacy endpoint that is defined as a binary variable indicating disease progression (death or respiratory failure) at Day 14 will be compared between the treatment groups based on the common risk difference resulting from the MH test considering the 4 strata out of the combinations of the 2 randomization stratification factors disease severity (moderate versus severe) and age-class (\leq 65 years versus >65 years).

Missing data on Day 14 resulting from study termination prior to Day 14 are not expected. However, in case they happen, such monotone missings will be imputed by multiple imputation using information from similar patients of the same treatment group assuming the missings are MAR. Missing post-baseline data for patients randomized but not treated will be imputed by BOCF. Intermediate missing data of Day 14 (ie, NIAID assessments prior Day 14 and at Day 28 are available, but only Day 14 is missing) will be imputed by LOCF. The comparison between the treatment groups will be performed on the ITT after imputation of missing values using the MH test. 95% confidence interval (CI) will be performed by imputation of missing values at Day 14 with 'progression' assuming that missings happen not at random (MNAR). A table with number and type/reason of missing values in the primary efficacy variable will be provided by treatment group on the ITT.

All above described analyses will be repeated on PPS as supportive analysis. Additionally a logistic regression model with treatment and the 2 stratification factors as covariables will be applied on the ITT as supportive analysis.

10.2. Key Secondary Efficacy Estimands and Analyses

10.2.1. Key Secondary Efficacy Endpoint 1

Similar MH analyses as for the main estimand of the primary efficacy endpoint will be applied to the main estimand and the second estimand of the first key secondary efficacy endpoint, which is defined as a binary variable indicating disease progression (death or respiratory failure) at Day 28. Prior to the analysis, missing data will be imputed as described in Section 7.2 of this SAP. A sensitivity analysis for the main estimand and the second estimand will be performed by imputation of missing values at Day 28 with 'progression' assuming MNAR. A table with number and type / reason of missing values in the first key secondary efficacy variable will be provided by treatment group on the ITT.

10.2.2. Key Secondary Efficacy Endpoint 2

Similar MH analyses will be applied to the main estimand and the second estimand of the second key secondary efficacy endpoint, which is defined as a binary variable indicating disease resolution (alive and have a score of 6, 7 or 8 on NIAID) at Day 28. Prior to the analysis, missing data on Day 28 will be imputed as described in Section 7.3 of this SAP. A sensitivity analysis for the main estimand and the second

This document is confidential.

estimand will be performed by imputation of missing values at Day 28 with 'no disease resolution' assuming MNAR. A table with number and type / reason of missing values in the second key secondary efficacy variable will be provided by treatment group on the ITT.

10.2.3. Key Secondary Efficacy Endpoint 3

A similar MH approach as described above will be applied also to the main estimand of the third key secondary efficacy endpoint, which is the all-cause mortality at Day 28. No missing data of life status on Day 28 is expected. However, in case of missing information life status will be imputed by death.

10.2.4. Key Secondary Efficacy Endpoint 4

The main estimand of the fourth key secondary efficacy endpoint 'Change of clinical status related to COVID-19 on Day 28 compared with baseline on the NIAID 8-point ordinal scale' will be compared using the risk difference between the treatment groups resulting from the analysis of covariance (ANCOVA) model with treatment and the 2 binary stratification factors severity and age-class as independent factors and the baseline value of NIAID as independent covariate. Prior to the analysis, missing data on Day 28 will be imputed as described in Section 7.5 of this SAP. A sensitivity analysis for the main estimand will be performed by imputation of missing values at Day 28 in both treatment groups using information from similar patients of the placebo group assuming MNAR. A table with number and type / reason of missing values in the fourth key secondary efficacy variable will be provided by treatment group on the ITT.

All above described analyses for the key secondary endpoints will be repeated on PPS as supportive analyses. Additionally a logistic regression model with treatment and the 2 stratification factors as covariables will be applied on the ITT as supportive analysis.

10.3. Other Secondary Efficacy Endpoints

No estimands are defined for other secondary efficacy endpoints. Missing life status will be imputed by death, however other missing data will not be imputed for the analysis of other secondary efficacy endpoints. Other secondary efficacy endpoints will be summarized and analyzed on the ITT.

The proportion of patients with disease resolution at Day 14 and the all-cause mortality rate at Day 14 and Day 60 will be analyzed using similar MH methods as described above for disease resolution at Day 28. Additionally, the cumulative proportion of patients with disease resolution will be plotted over time.

A similar ANCOVA approach as described above (10.2.4.) will be applied for the analysis of the change of clinical status related to COVID-19 on Day 14 compared with baseline on the NIAID 8-point ordinal scale. The endpoints considering the proportion of patients requiring invasive ventilation (mechanical ventilator and/or ECMO) or who are not alive, the proportion of patients in each NIAID category, and the proportion of patients alive and testing negative for COVID-19 on Day 14, Day 28 and Day 60, respectively, will be compared between the treatment groups using MH tests. Overall survival, time to (first) improvement of at least 1 category on the NIAID scale and total hospitalization duration (from baseline to discharge; with death censored on last day of the observed period - at Day 28 or Day 60, respectively - depending on the analyses) will be summarized using Kaplan-Meier estimates and will be compared between treatment groups using logrank tests. Additionally, Cox proportional hazards model will be applied with treatment and the 2 stratification factors as independent variables.

The odds ratio between MP1032 + SoC and placebo + SoC of the number of patients with clinical status improvement from baseline on the NIAID 8-point ordinal scale (ie, an improvement of at least 1 category)

This document is confidential.

SAP Text Version: 2.0, 31-Aug-2022 Controlled Document ID CCC , Effective Date 31-Aug-2020 Filing requirements: TMF

Page 37 of 56

at Day 14 and Day 28 will be analyzed using a logistic regression with consideration of the 2 stratification factors.

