4.1. Brief Description

This is a Phase IIa, randomized, double-blind, placebo-controlled, multicenter, proof-of-concept study designed to assess the potential efficacy and safety of 300 mg MP1032 twice daily (BID) plus SoC versus placebo plus SoC in hospitalized adults with moderate to severe COVID-19.

Approximately 40 sites worldwide will participate in this study.

Approximately 140 patients will be screened to randomize approximately 120 patients in 2:1 ratio as follows:

- Arm A (300 mg MP1032 BID plus SoC): approximately 80 patients
- Arm B (placebo BID plus SoC): approximately 40 patients

The stratification factor for randomization will include baseline COVID-19 severity (moderate and severe) and age-class (≤65 years and >65 years). COVID-19 severity will be determined using the following criteria:

- Moderate COVID-19:
 - Positive severe acute respiratory syndrome coronavirus type 2 (SARS-CoV-2) testing by standard reverse-transcription polymerase chain reaction (RT-PCR) assay or equivalent test
 - Symptoms of moderate illness with COVID-19, which could include any symptom of mild illness or shortness of breath with exertion
 - Clinical signs suggestive of moderate illness with COVID-19, such as respiratory rate ≥20 breaths per minute, saturation of oxygen (SpO₂) >93% (on room air at sea level, if possible), heart rate ≥90 beats per minute
 - No clinical signs indicative of severe or critical COVID-19
- Severe COVID-19:
 - Positive SARS-CoV-2 testing by standard RT-PCR assay or equivalent test
 - Symptoms suggestive of severe systemic illness with COVID-19, which could include any symptom of moderate illness or shortness of breath at rest, or respiratory distress
 - Clinical signs indicative of severe systemic illness with COVID-19, such as respiratory rate ≥30 breaths per minute, heart rate ≥125 beats per minute, SpO₂ ≤93% (on room air at sea level, if possible), partial pressure of oxygen (PaO₂)/ fraction of inspired oxygen (FiO₂)<300, or diagnosed with acute respiratory distress syndrome ([ARDS] according to the Berlin definition; see Table 3 in the Protocol)
 - No criteria met for critical COVID-19

To standardize the assessment of COVID-19 severity, respiratory rate, SpO₂, and heart rate will be measured when the patient is on room air at sea level (ie, no supplemental oxygen, if possible) and at rest for at least 5 minutes. If possible, the site should collect the information from each patient at the same time each day (±1 hour).

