4.3. Determination of Sample Size

The primary efficacy endpoint 'proportion of patients with disease progression on Day 14' is assumed to be 10% in the 300 mg MP1032 BID plus SoC treatment group (Arm A) and 30% in the placebo plus SoC treatment group (Arm B). Using the Chi-square test with type I error alpha=10% two-sided for this proof-of-concept study and 2:1 randomization ratio, 114 patients (76 in Arm A and 38 in Arm B) are required to achieve a statistical power of 83%. Considering about 5% early study terminations, the necessary sample size for randomization results in 120 patients in total (80 in Arm A and 40 in Arm B). If during the conduct of the study the early study termination rate is higher than the estimated 5%, then an increase in the randomized number of patients may be necessary.

Sample size estimation is performed using nQuery 8, Version 8.6.1.0.

A subset of randomized patients will be consented for the collection of blood samples for PK measurements. The PK subset consists of approximately 20 patients from the 300 mg MP1032 BID plus SoC group and approximately 10 patients from the placebo plus SoC group, up to a total of approximately 30 patients.

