5.3. Other Secondary Efficacy Endpoints

The other secondary efficacy endpoints of this study are:

This document is confidential.

SAP Text Version: 2.0, 31-Aug-2022 Controlled Document ID: CCC , Effective Date 31-Aug-2020 Filing requirements: TMF

Page 23 of 56

- Proportion of patients with disease resolution on Day 14. Disease resolution is defined as patients who are alive and have a score of 6, 7, or 8 on the NIAID 8-point ordinal scale (as listed above).
- All-cause mortality rate at Day 14 and Day 60
- Change of clinical status related to COVID-19 on Day 14 compared with baseline according to the NIAID 8-point ordinal scale (as listed above)
- Proportion of patients requiring invasive ventilation (mechanical ventilator and/or ECMO), or who
 are not alive on Day 14 or Day 28
- · Proportion of patients in each category of the NIAID 8-point ordinal scale
- Time to (first) improvement of at least 1 category on the NIAID 8-point ordinal scale (until Day 28).
 Patients who did not improve at least 1 category on the NIAID scale or deaths before Day 28 will be censored at Day 28.
- The odds ratio between MP1032 and SoC and placebo and SoC of the number of patients with clinical status improvement from baseline on the NIAID 8-point ordinal scale (ie, an improvement of at least 1 category) at Day 14 and Day 28
- Total duration of hospitalization (from baseline to discharge; with death censored on the last day of the observed period – at Day 28 or Day 60, respectively)
- Proportion of patients alive and testing negative for COVID-19 on Day 14, Day 28 and Day 60

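### The log-rank tests in Section 10.3 omit the randomisation strata, and the Day 28 censoring rule for time to improvement, read literally, counts living early leavers as observed non-improvers (minor)

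*SAP*

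**What the plan says.** Test. Section 10.3 says that overall survival, time to first improvement of at least one NIAID category and total hospitalization duration "will be summarized using Kaplan-Meier estimates and will be compared between treatment groups using logrank tests". No strata are named. The next sentence adds, for the same endpoints, that a "Cox proportional hazards model will be applied with treatment and the 2 stratification factors as independent variables".

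Randomisation. Section 4.1: "The stratification factor for randomization will include baseline COVID-19 severity (moderate and severe) and age-class". Section 4.4 repeats this. The Mantel-Haenszel analyses of the primary and first three key secondary endpoints use the four resulting strata. The ANCOVA and the logistic models use the two factors.

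Censoring. For time to improvement, Section 5.3 says: "Patients who did not improve at least 1 category on the NIAID scale or deaths before Day 28 will be censored at Day 28". It has no separate clause for a patient who leaves the study alive and unimproved before Day 28. Hospitalization duration has its own rule, which covers deaths only ("with death censored on last day of the observed period"). For all other secondary endpoints, Section 10.3 says: "Missing life status will be imputed by death, however other missing data will not be imputed".

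**The concern.** There are two separate points.

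1. When randomisation is balanced within prognostic strata, a test that ignores them uses a variance that is too large for the design. It then rejects less often than its nominal level and loses power. It also answers a slightly different question from the adjusted Cox model beside it. The SAP does not say which result is to be read if the two fall on opposite sides of the 10% level.

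2. Holding deaths at Day 28 is a defensible way to record that they never improved. Applied to everyone who did not improve, the same rule keeps a living patient who withdraws on Day 5 in the risk set for 28 - 5 = 23 unobserved days. In effect this imputes non-improvement, which sits badly with the statement in Section 10.3 that missing data other than life status are not imputed. It pulls the improvement curve down. The Cox model does not repair this, because it uses the same censored times.

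**Working it through.** **The plan's own figure.** Section 4.3 gives 10% v 30%, 76 + 38 patients, two-sided alpha 10%, power 83%. Pooled rate = (38 × 0.30 + 76 × 0.10)/114 = 0.1667. SE under the null = √[0.1667 × 0.8333 × (1/38 + 1/76)] = 0.0740. SE under the alternative = √(0.21/38 + 0.09/76) = 0.0819. Power = Φ[(0.20 - 1.645 × 0.0740)/0.0819] = Φ(0.955) = 83.0%. Then 114/0.95 = 120. Both figures reproduce. The SAP states no power for any time-to-event endpoint, so what follows rests on assumptions.

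**Log-rank with and without strata.** From the SAP: 120 patients, 2:1, four strata, two-sided 10%, 5% leaving. Assumed: improvement hazard ratio 1.6, 85% improved by Day 28 in moderate younger controls (daily hazard -ln(0.15)/28 = 0.068), 50% severe, 40% older, blocks of 6, exponential times, daily assessment, non-informative leaving spread over the 28 days. The statistic is Z = U/√V, with U = Σ(d₁ - d·n₁/n) and V = Σ d(n₁/n)(1 - n₁/n)(n - d)/(n - 1). The stratified version sums U and V over the strata before dividing. There were 2,000 runs per row, with Day 28 censoring kept, so that only the test changes.

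| Assumed strata HR (severe, older) | Power, unstratified | Power, stratified | Change | Size, unstratified | Size, stratified |
|---|---|---|---|---|---|
| none (1, 1) | 72.0% | 70.2% | -1.8 | 9.7% | 10.0% |
| weak (0.7, 0.8) | 67.3% | 68.1% | +0.8 | 9.3% | 9.3% |
| moderate (0.5, 0.7) | 59.5% | 63.7% | +4.2 | 9.2% | 10.7% |
| strong (0.35, 0.6) | 48.4% | 57.7% | +9.3 | 7.0% | 9.4% |

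Monte Carlo error is about 1 point for power and √(0.1 × 0.9/2000) = 0.7 points for size.

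A second simulation, with the same strata assumptions, no leaving and 1,000 runs (error about 1.5 points), adds the planned Cox model. Power for unstratified log-rank / stratified log-rank / Cox:

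- none: 74 / 72 / 74%
- weak: 69 / 69 / 70%
- moderate: 61 / 67 / 68%
- strong: 50 / 62 / 64%

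The gain from stratifying is here -2, 0, +6 and +12 points. Across the two simulations it is about -2 to +1 (none or weak), +4 to +6 (moderate) and +9 to +12 (strong).

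**Day 28 censoring.** Let F be the true proportion improved by Day 28, d the proportion leaving, and improvement times exponential with 28λ = -ln(1 - F). If leaving is uniform over 28 days, a leaver is seen to improve before leaving with probability p = 1 - F/(28λ). The Day 28 estimate is then (1 - d)F + d·p, so the bias is -d(F - p).

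- F = 0.80, d = 0.05: 28λ = 1.609, p = 1 - 0.80/1.609 = 0.503, bias = -0.05 × 0.297 = -1.5 points.
- F from 0.60 to 0.90: -1.3 to -1.5 points at 5% leaving, -2.5 to -3.0 at 10%, -5.1 to -5.9 at 20%.
- All 5% leaving in week 1: -2.4 to -3.1 points.
- Limit if all leave at the start: -d·F, that is -3.0 to -4.5 points at 5%.

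Equal leaving hardly moves the gap between arms. With 5% leaving in each arm, true values of 90% and 80% become 88.55% and 78.51%, a gap of 10.0 points. Unequal leaving does move it. At 15% v 5% and F = 0.80 the biases are -4.46 and -1.49, a false gap of about 3.0 points. In the simulation under the null with 15% v 5% leaving (either way round, moderate strata), the unstratified test rejected in 9.5% and 9.8% of runs under the Day 28 rule, against 8.5% and 9.0% with censoring at last assessment.

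**Both changes together**, 5% leaving: power 72.0% → 72.0% (none), 67.3% → 68.9% (weak), 59.5% → 64.6% (moderate), 48.4% → 58.8% (strong).

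**The case against.** The strongest answer on the first point is the Cox model. It adjusts for both factors, covers the same three endpoints, and in the second simulation had at least the power of the stratified log-rank in every scenario. An unstratified log-rank after stratified randomisation is also valid. It falls clearly below its nominal level only with strong strata (7.0%), and stratifying can cost about 2 points if the strata carry no information. The strata effects are assumptions. Improvement is counted from each patient's own baseline category, so a strong severity effect is not self-evident. Only time to improvement was simulated, not survival or hospital stay. All of this stands. What remains is that the log-rank and the Cox model treat the strata differently and the SAP does not rank them.

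On the second point, few patients should be affected. The SAP plans for about 5% early termination. It does not expect Day 14 data to be missing through study termination. Patients who only stop study drug can remain in follow-up. Discharge moves a hospitalized patient to category 7 or 8 and so counts as improvement. The sentence on not imputing other missing data could also be read as taking early leavers out of the Day 28 rule. This limits the size of the effect, but two sentences that can be read against each other still leave the programmer to choose.

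A reader might infer more than the documents support:

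- That stratification is ignored for these endpoints. It is not, given the Cox model.
- That every binary endpoint uses the four strata. In Section 10.3 some are assigned only MH tests with no strata named, and one uses logistic regression.
- That the Day 28 rule distorts all three curves. It belongs to time to improvement. Missing life status is imputed as death, and hospital stay has its own wording.
- That a gap of about 6 points between arms is likely. That needs 10% v 0% leaving, all in week 1, which nothing in the SAP suggests.

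**Conclusion.** The point holds in limited form, and its importance is minor. The log-rank p-values are valid but conservative and less powerful if severity and age-class are prognostic. The cost is between nothing and about 12 points of power across the assumed range, and the adjusted Cox model already recovers it. The Day 28 rule, read literally, lowers the estimated proportion improved by about 1.5 points at the SAP's own 5% early termination (about 3 if all leave in week 1, at most 4.5). It creates a difference between arms only if leaving differs by arm. The documents do not support a reading of inflated type I error or of an invalid analysis. The power figures rest on the assumed hazard ratio of 1.6, strata effects and case mix. The curve figures rest on exponential improvement times and non-informative leaving. The primary and key secondary analyses are untouched. These are other secondary endpoints without multiplicity control in a descriptive proof-of-concept study.

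**What to change.** In Section 10.3, state that the log-rank tests are stratified by the four randomisation strata, in line with the adjusted Cox model, and say which of the two is the main result. The downside is a slight loss of power if the strata turn out not to be prognostic.

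In Section 5.3, restrict Day 28 censoring for time to improvement to deaths and to patients followed to Day 28 without improving. Censor patients who leave alive and unimproved at their last NIAID assessment. Table 1 schedules the scale daily to Day 14, at Day 28 and at early termination, so the date can be derived. The same edit can usefully say how leavers are handled for hospitalization duration.

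The cost is two or three sentences before unblinding, with no new data.

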10.4. Exploratory Efficacy Endpoints

No estimands are defined for exploratory efficacy endpoints. Exploratory efficacy endpoints will be summarized by descriptive statistics on the ITT, only. No statistical comparison will be performed. Some exploratory efficacy endpoints are defined in a subgroup of the randomized patients: potential bias resulting from this aspect will be considered in the interpretation of respective summaries by treatment.

The time to recovery of all at baseline present COVID-19 symptoms (stuffy or runny nose, sore throat, red or irritated eyes, shortness of breath, cough, low energy or tiredness, muscle or body aches, headache, chills or shivering, feeling hot or feverish, nausea, and number of times of vomit, times of diarrhea, sense of smell, sense of taste in the last 24 hours) will be presented by Kaplan-Meier estimates and figure. The change from baseline will be presented in shift tables for each single symptom with the number and percentage of patients in each category at post-baseline assessment time-point compared to baseline for each treatment group. Number of symptoms will be summarized by visit and treatment group.

Total number of days in ICU and duration of invasive mechanical ventilation, and/or ECMO will be descriptively summarized by treatment group using mean days with 90% confidence intervals and additionally by median days and quartiles. To consider death sufficiently unfavorable in these measures, in case of death the duration of the respective measure will be considered with the longest duration possible. Eg, if a summary of the first 28 days is presented, then death prior to Day 28 will be considered as duration 28 days, and if the summary includes also follow-up period until Day 60, then death prior to Day 60 will be considered as duration 60 days. Both summaries (up to Day 28 and up to Day 60) will be provided.

Saturation of oxygen (SpO2)/fraction of inspired oxygen (FiO2) ratio (for patients alive) will be summarized for actual values and change from baseline by treatment and visit.

For HRQoL assessments at discharge and Day 60, the EQ index value and the EQ VAS, both based on the EQ-5D-5L questionnaire will be calculated and summarized by visit and treatment group. Additionally, the change at Day 60 from discharge will be summarized by treatment group. For countries without a published index value set, the published value set from the geographically closest country will be used.

This document is confidential.

SAP Text Version: 2.0, 31-Aug-2022 Controlled Document ID: CC , Effective Date 31-Aug-2020 Filing requirements: TMF

Page 38 of 56

11. Pharmacokinetics

The Pharmacokinetic Analysis Set will be used for the analyses specified in this section.

This SAP describes the method of deriving PK using non-compartmental analysis applying appropriate software, ie, Phoenix[™] WinNonlin[®] (Version 8.0 or higher, Certara Corporation), and all other analyses and summaries using SAS[®] (Version 9.4 or higher, SAS Institute Inc.), which will be presented in CSR.

The PK analyses will be conducted for MP1032 in plasma and will include a listing, summary, figure of concentrations, and derived PK parameters as described below.

